9.2. Sample Size Considerations

9.2.1. Sample Size Assumptions

Part 1: Dose Escalation

The total number of subjects to be enrolled in the dose escalation phase of Part 1 will depend on the number of subjects needed to characterize individual dose combination cohorts. The sample size is not driven by statistical considerations. However, it is anticipated that approximately 10-12 evaluable subjects will be enrolled.

Part 2: Expansion Cohorts

To determine the maximum sample size for Arm A or Arm B, Bayesian predictive adaptive design will be used for testing hypotheses:

H_0 : CBR \leq 30%

H_A : CBR \geq 50%

When maximum sample size is 28, the design will have a Type I error (α) of 0.099 and 81% power with the probability of termination is 0.90 when the treatment is futile and probability of early termination 0.183 when the treatment is effective (true RR=0.5).

In Part 2, a maximum of 28 subjects will be enrolled in Arm A and Arm B expansion cohort, respectively. If both arms enroll the maximum number of subjects, this will result in 56 subjects total randomized to Arm A and Arm B with 1:1 randomization ratio.

Enrollment into Arm A or Arm B may be halted early based on results from interim analyses incorporating emerging response data. Response data from a minimum of 10 evaluable subjects will be required per arm before it may discontinue enrollment for futility.

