9.1.2. Part 2: Disease-Specific Expansion Cohorts

The primary goal of Part 2 is to evaluate disease-specific clinical activity in subjects with GSK2879552, alone or in combination with azacitidine, in adult subjects with MDS. Clinical activity is defined as a clinical benefit rate (% of subjects achieving CR, PR, HI or SD [per 2006 IWG criteria]). This will be conducted by testing the null hypothesis that $P_0 \leq 0.3$ versus the alternative that $P_1 \geq 0.5$, Subjects in Part 1 and Part 2 treated with the same starting dose will be analyzed together.

The Part 2 portion of the study will employ a Bayesian predictive adaptive design [Lee, 2008] for Arm A and Arm B separately that allows the trial to be monitored more frequently at multiple stages. The criteria will be based on a historically unimportant response rate of 30% versus a response rate of interest of 50%. Bayesian statistics will be employed to calculate the predictive probability that the response rate $\geq 50\%$ and $\geq 30\%$ at interim assuming a Beta prior for the Binomial distributed data. Predictive probability calculates the probability that the response rate $\geq 50\%$ or $\geq 30\%$ at the end of Part 2 given the responses that are currently being observed at interim. It predicts what is likely to happen at the end of Part 2 so it is more meaningful and straightforward than posterior probability. A weak prior Beta (0.005, 0.005) is used, which is equivalent to the information present in 0.01 subjects. The first interim analysis may be conducted when at least 10 subjects are recruited for each Arm. Futility interim analysis decision rules for the 10th to 28th evaluable subjects, specifying the number of subjects with clinical activity (CR, PR, HI or SD) needed for continuing enrolment or stopping for futility when total sample size is up to 28, is presented in Table 5. These rules are intended as a guideline. Actual decisions will depend on the totality of the data.

Table 5 Decision Making Criteria for Futility

| Number of Evaluable Subjects | ≤ This Number of Responses to Stop Early for Futility | Probability of continuing enrolling when CBR=0.3 | Probability of continuing enrolling when CBR=0.5 |
|------------------------------|---|--|--|
| 10 | 1 | 0.8507 | 0.9893 |
| 12 | 2 | 0.7363 | 0.9783 |
| 14 | 3 | 0.6242 | 0.9655 |
| 16 | 3 | 0.6242 | 0.9655 |
| 18 | 4 | 0.5739 | 0.9620 |
| 20 | 5 | 0.5087 | 0.9566 |
| 22 | 6 | 0.4414 | 0.9500 |
| 24 | 8 | 0.2601 | 0.9103 |

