| 26 | 9 | 0.2059 | 0.8927 |
| 28 | 11 | 0.0000 | 0.0000 |

For the separate interim looks in each cohort in Part 2, the enrollment for that cohort may be stopped due to futility if the predictive probability that the confirmed response rate $\geq 30\%$ (historical control) is small (e.g., less than a 2% chance for a total sample size of 28 subjects). Enrollment may also be stopped due to futility if the equivalent of less than 2 responses is observed in the first 10 enrolled evaluable subjects in that cohort or less than 3 responses are observed in the first 12 evaluable subjects. The evaluable subject is defined as a subject, who has either progressed, withdrew from the study, was lost to follow-up, or is ongoing and has completed at least one post treatment disease assessment. For example, when there are 10 evaluable subjects available at the time of interim analysis with only one response, then the Arm may be stop for futility. Otherwise, the enrolment of the respective Arm will continue to the target sample size.

When the total sample size in a treatment arm is 28 and at least 12 responders out of 28 subjects are observed, we can claim null hypothesis is rejected.

No formal hypotheses are set up to compare the activity between Arm A and Arm B. The CBR and ORR will be reported for both arms separately at the end of Part 2.

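### The early-termination figure in Section 9.2.1 is really the type II error, and the futility criterion worded in Section 9.1.2 is not the one that generates Table 5

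*Protocol*

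**What the plan says.** Section 9.1.2 sets the design for each arm: "The criteria will be based on a historically unimportant response rate of 30% versus a response rate of interest of 50" percent. On the prior it says: "A weak prior Beta (0.005, 0.005) is used, which is equivalent to the information present in 0.01 subjects". Table 5 then lists futility boundaries for every second evaluable subject from 10 to 28, with the probability of continuing at CBR 0.3 and 0.5. The last interim row (evaluable subjects, stopping boundary, two continuing probabilities) is "26 | 9 | 0.2059 | 0.8927". The row for 28 stops at 11 or fewer, and the null hypothesis is rejected with at least 12 of 28.

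Below the table, Section 9.1.2 puts the criterion in words. A cohort may stop if the predictive probability that the confirmed response rate is at least 30% "is small (e.g., less than a 2% chance for a total sample size of 28 subjects"). The same paragraph also allows stopping with fewer than 2 responses in the first 10 evaluable subjects, or fewer than 3 in the first 12.

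Section 9.2.1 states a type I error of 0.099 and power of 81%, "with the probability of termination is 0.90 when the treatment is futile and probability of early termination 0.183 when the treatment is effective" (true rate 0.5).

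**The concern.** There are two separate mismatches.

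The first is in the stated operating characteristics. Table 5 already shows how often an arm survives the last interim look. The complement is the early-termination probability, and it is not the figure in Section 9.2.1. A reader would think an effective arm has an 18% chance of being closed before 28 subjects, when the table implies 11%.

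The second is in the rule itself. If the predicted event is an end-of-Part-2 rate of at least 30%, an arm with 9 responders among 26 has already met it, because 9/28 is 32%. Table 5 nevertheless calls for stopping there. Section 9.3.2.1 sends each cohort's futility decision back to Section 9.1.2, so a team applying the sentence and a team applying the table could decide differently on the same data, for the primary Part 2 endpoint.

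**Working it through.** **Inputs**

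- Null rate 0.30, rate of interest 0.50, prior Beta(0.005, 0.005), Table 5 boundaries, success at 12 or more of 28: Section 9.1.2.
- Maximum 28 per arm, first look at 10 evaluable subjects, stated alpha, power and termination figures: Section 9.2.1.

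**Step 1: reproduce the plan's own figures.** Carry the binomial distribution of responders through the looks and remove the paths at or below each boundary. First look:

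- CBR 0.3: 1 − (0.7^10 + 10 × 0.3 × 0.7^9) = 1 − (0.0282 + 0.1211) = 0.8507
- CBR 0.5: 1 − 11/1024 = 0.9893

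Both agree with Table 5. Continuing the recursion reproduces every continuing probability from 10 to 26 to four decimals. The probability of 12 or more of 28 without an earlier stop is 0.0991 at CBR 0.3 (stated alpha 0.099) and 0.8174 at CBR 0.5 (stated power 81%).

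**Step 2: termination probabilities.**

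| | CBR 0.3 | CBR 0.5 |
|---|---|---|
| Stop before 28 | 1 − 0.2059 = 0.794 | 1 − 0.8927 = 0.107 |
| Reach 28, then 11 or fewer | 0.107 | 0.075 |
| Not rejecting the null, total | 1 − 0.0991 = 0.9009 | 1 − 0.8174 = 0.1826 |
| Section 9.2.1 | 0.90 | 0.183 |

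The figures in Section 9.2.1 are the total row. The one explicitly labelled as early termination is 0.183/0.107 = 1.7 times the value implied by Table 5.

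**Step 3: the criterion as worded.** With x responders among n, the remaining 28 − n outcomes are beta-binomial with parameters 0.005 + x and 0.005 + n − x. A final observed rate of at least 30% means 9 or more of 28, since 0.30 × 28 = 8.4. The largest x with predictive probability below 2% is:

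| n | 10 | 12 | 14 | 16 | 18 | 20 | 22 | 24 | 26 |
|---|---|---|---|---|---|---|---|---|---|
| Table 5 | 1 | 2 | 3 | 3 | 4 | 5 | 6 | 8 | 9 |
| At least 9/28, below 2% | 1 | 1 | 1 | 2 | 3 | 3 | 4 | 5 | 6 |
| At least 12/28, below 2% | 1 | 2 | 3 | 4 | 4 | 5 | 6 | 8 | 9 |
| At least 12/28, below 1.9% | 1 | 2 | 3 | 3 | 4 | 5 | 6 | 8 | 9 |

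The explicit rule of fewer than 3 in 12 raises the second row to 2 at n = 12. The worded criterion then still differs from Table 5 at the seven looks from 14 to 26.

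Two points where Table 5 stops:

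- 9/26: at least 9 of 28 is already certain, so the predictive probability is 1.0.
- 8/24: 1 − (16.005 × 17.005 × 18.005 × 19.005)/(24.01 × 25.01 × 26.01 × 27.01) = 1 − 0.221 = 0.78.

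**Step 4: what Table 5 is consistent with.** Take the predicted event as 12 or more of 28. At 9/26 the most that can be reached is 11, so the probability is 0. At 8/24 all four remaining subjects must respond: (8.005 × 9.005 × 10.005 × 11.005)/(24.01 × 25.01 × 26.01 × 27.01) = 0.0188, and the table stops. At 4/16 the probability is 0.0192, and the table continues. Any cutoff between 0.0188 and 0.0192 reproduces every row.

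**Step 5: size of the difference.** Same recursion, success at 12 or more of 28:

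| Rule | Early stop, CBR 0.3 | Early stop, CBR 0.5 |
|---|---|---|
| Table 5 | 0.794 | 0.107 |
| Worded criterion with the 12-subject rule | 0.401 | 0.025 |

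**The case against.** **The stated figures can be read as boundary crossings.** Table 5 carries 28 as a futility row, so the probability of ending at or below any listed boundary is 0.9009 and 0.1826, exactly the stated pair. For the futile case Section 9.2.1 says termination, without the word early. This stands: 0.90 is loosely worded and not miscalculated. It does not rescue 0.183, which is called early termination, because failing at the full 28 is not early. Monitoring after every subject does not rescue it either: the 12-of-28 criterion at 2%, applied at each n from 10 to 27, gives early stopping of 0.857 and 0.148.

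**Success was meant all along.** Section 4.1 bases Part 2 on the predictive probability of success, Section 9.1.2 defines success as 12 of 28, and its worked examples at 10 and 12 subjects agree with Table 5. This shows what was probably intended. But the sentence that states the criterion names a response rate of at least 30%, and no choice of cutoff makes an event with predictive probability 1.0 trigger a stop.

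**Everything is a guideline.** The 2% is given as an example, enrolment may be stopped, and the totality of data decides. This lowers the weight of the point. It also disposes of a reading that the 16-subject row, "16 | 3 | 0.6242 | 0.9655", is an error: 0.0192 against an illustrative 2% is a rounding of the cutoff, and the row fits the stated alpha and power.

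**Conclusion.** The point holds as a moderate text correction. The value given as early termination at CBR 0.5 is the type II error, 0.183; Table 5 implies 0.107. The companion 0.90 is 1 − alpha; Table 5 implies 0.794 for stopping before 28. The worded futility criterion, taken as a final observed rate of at least 30%, contradicts the table from 14 to 26 evaluable subjects and would stop an inactive arm early about half as often (0.40 against 0.79).

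The figures assume looks at the sizes listed in Table 5, binding boundaries and the stated prior. The contrast in early stopping also rests on reading at least 30% as at least 9 of 28 and on a 2% cutoff. The contradiction at 9/26 does not depend on the cutoff.

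A reader might infer that the design itself is miscalculated. The documents do not support that: Table 5's interim probabilities, alpha and power all reproduce, and neither 28 subjects nor the 12-responder criterion needs to change. The mislabelled 0.183 overstates the risk of closing an effective arm early, and no decision rule uses it.

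**What to change.** In Section 9.2.1, give the probability of early termination (before 28 subjects) as 0.79 at CBR 0.3 and 0.11 at CBR 0.5, and relabel 0.90 and 0.183 as the probability of not rejecting the null hypothesis.

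In Section 9.1.2, define the predicted event as at least 12 responders out of 28, and state the cutoff that Table 5 uses: about 1.9%, anywhere between 0.0188 and 0.0192.

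Leave Table 5 as it is, including the row for 16. The cost is a few sentences. Boundaries, alpha, power and sample size do not move. The correction should be in place before the first futility look.

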6.3. Treatment Assignment

In Part 1, subjects will be assigned to Arm A (GSK2879552 only) or Arm B (GSK2879552 in combination with azacitidine) according to the investigator discretion and/or the availability of the enrolment slot.

In Part 2, subjects will be assigned to Arm A (GSK2879552 only) or Arm B (GSK2879552 in combination with azacitidine) in accordance with the randomization schedule generated by Clinical Statistics, prior to the start of the study, using validated internal software.

Subjects will be identified by a unique subject number that will remain consistent for the duration of the study.

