6.4. Blinding

This will be an open-label study

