9.3.2.1. Part 2 Cohort Expansion

Interim data will be evaluated to monitor efficacy and safety. Enrollment may be stopped early for futility, should various criteria occur based on accrued data. The decision criteria for early stop for futility based on Bayesian Adaptive design are described in Section 9.1.2. The decision will be made for each individual cohort.

The study population used for decision-making at the interim analyses during Part 2 (Expansion Cohort) will be termed All Evaluable Subjects defined in Section 9.1.2. This will be the population for Bayesian adaptive design described in Section 9.1.2 and summaries of response if data warrant. Any evaluable subject from Part 1 of the study who has the same initial dose as in Part 2 will be included in this analysis. Because subjects enroll at different times, not all subjects will have been on the study long enough to have a single or multiple disease assessments. Since disease assessments are to be completed every 4 weeks, subjects who have at least one post-baseline disease assessment or have progressed or died or permanently withdraw from the study will be included in this population.

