9.4.1. Clinical Activity Analyses

The clinical benefit rate (CBR) is defined as the percentage of subjects with a Complete Remission (CR), marrow complete remission (mCR) or a Partial Remission (PR) or a Hematologic Improvement (HI) or Stable Disease (SD) at any time as per disease-specific criteria ([Appendix 5](#) and [Appendix 6](#)). Subjects with unknown or missing response will be treated as non-responders, i.e. these subjects will be included in the denominator when calculating the percentage. The number and types of responses, as outlined in IWG criteria [[Cheson, 2006](#)], will be listed and summarized separately, as appropriate.

The ORR will be reported at the interim and final analysis for each arm specified in Part 2 as well as all evaluable subjects in Part 1 treated at or above RP2D. Part 1 and Part 2 subjects who received the same dose within the same treatment arm may be combined together in the analysis. The estimates along with 95% exact confidence interval (CI) will be provided.

The CBR and ORR differences between the two cohorts will be provided along with corresponding 95% CI. A chi-square test will be used to test for differences between arms if data warrant.

Duration of response is defined as the subset of subjects who show a response (CR, mCR, PR, or HI), the time from first documented evidence of response until the first documented sign of disease progression or death. Duration of response will be summarized descriptively for each arm, if data warrant, using Kaplan-Meier medians and quartiles. Details on rules for censoring will be provided in the RAP.

For the analysis of **Progression-free survival (PFS)**, if the subject received subsequent anti-cancer therapy prior to the date of documented events, PFS will be censored at the last adequate assessment (e.g. assessment where visit level response is CR, mCR, PR, HI or SD) prior to the initiation of therapy. Progressive disease (PD) will also be defined per standard criteria. Otherwise, if the subject does not have a documented date of events, PFS will be censored at the date of the last adequate assessment. Further details on rules for censoring will be provided in the RAP. PFS will be summarized by arm and dose using Kaplan-Meier quantile estimates along with 2-sided 95% CIs at the time of final analysis, if data warrant.

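### The planned Arm A versus Arm B difference is not limited to subjects randomised while both arms were open, although either arm can close for futility on its own

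*Protocol*

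**What the plan says.** Part 2 subjects are assigned 1:1 to GSK2879552 alone (Arm A) or with azacitidine (Arm B), "in accordance with the randomization schedule generated by Clinical Statistics, prior to the start of the study" (6.3). On blinding, the protocol states "This will be an open-label study" (6.4).

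The Bayesian predictive design is run "for Arm A and Arm B separately that allows the trial to be monitored more frequently at multiple stages" (9.1.2), against a "historically unimportant response rate of 30% versus a response rate of interest of 50" per cent. Section 9.2.1 adds "Enrollment into Arm A or Arm B may be halted early based on results from interim analyses incorporating emerging response data", and 9.3.2.1 says of futility "The decision will be made for each individual cohort". Under 9.1.2, an arm that does not meet the futility rule goes on to its target of 28.

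On the comparison, 9.4.1 commits to this: "The CBR and ORR differences between the two cohorts will be provided along with corresponding 95% CI". A chi-square test between arms may follow if the data warrant it. Section 9.3.1 evaluates clinical activity in all treated subjects. Section 9.4.1 also lets Part 1 and Part 2 subjects on the same dose in the same arm be combined, and in Part 1 the arm was chosen by investigator discretion or slot availability (6.3).

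Section 9.1.2 sets no formal hypothesis between the arms and has CBR and ORR reported for each arm separately.

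**The concern.** With two arms and separate futility decisions, closing one leaves a single destination for everyone who follows. From that date nothing is randomised. Because the study is open label, site and subject know the treatment before enrolment. If the difference in 9.4.1 is computed on all treated subjects, as the text reads, the arm that stayed open contributes two kinds of subject: those randomised alongside the other arm, and those enrolled later with no concurrent counterpart. Any change in case mix over calendar time, or in who is offered the trial once the treatment is known, then enters the difference as if it were a treatment effect. Part 1 subjects, if pooled, add a second non-randomised component.

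What is at stake is how the between-arm estimate, its interval and any p-value can be read. Part 2 is described as randomised, so readers may take the contrast as randomised evidence. The per-arm decisions are not at stake.

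**Working it through.** **Inputs.** From 9.1.2 and Table 5: stop an arm if responses are at most 1/10, 2/12, 3/14, 3/16, 4/18, 5/20, 6/22, 8/24, 9/26; success is at least 12/28. From 9.2.1: maximum 28 per arm, 1:1 allocation, null CBR 30%, target 50%.

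**Method.** Exact forward recursion of the number of responses, dropping paths at or below the bound at each look.

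**Reproducing the plan's figures.** Every continuation probability printed in Table 5 from n = 10 to n = 26 is matched to four decimals (0.8507 down to 0.2059 at 30%; 0.9893 down to 0.8927 at 50%). The rejection probability is 0.0991 at 30% and 0.8174 at 50%, in line with the stated "Type I error (α) of 0.099 and 81% power".

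**Chance that one arm stops before 28.**
- At CBR 30%: 1 − 0.2059 = 0.794
- At CBR 50%: 1 − 0.8927 = 0.107

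**Crossing the two arms as independent.**
- A at 30%, B at 50%, A stops early and B reaches 28: 0.7941 × 0.8927 = 0.709
- Both at 30%, exactly one stops early: 2 × 0.7941 × 0.2059 = 0.327
- Both at 50%, exactly one stops early: 2 × 0.1073 × 0.8927 = 0.192

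**Number of non-concurrent subjects (A at 30%, B reaching 28).** The stopping probabilities for A at n = 10, 12, 14, 18, 20, 22, 24, 26 are 0.1493, 0.1144, 0.1121, 0.0503, 0.0652, 0.0673, 0.1813, 0.0542 (none at 16).
- Mean stopping size given an early stop: 13.89 / 0.7941 = 17.5
- Non-concurrent subjects in B: 28 − 17.5 = 10.5
- As a share of B: 10.5 / 28 = 37.5%

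**Bias.** If the later subjects' underlying CBR differs by d points from that of the concurrent subjects, the all-subject difference shifts by 0.375 × d. The documents give no d. As an assumption only, d from 10 to 20 points gives 3.8 to 7.5 points.

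**Effect of restricting the comparison.** The approximate 95% half-width is 1.96 × √(pA(1−pA)/nA + pB(1−pB)/nB).
- 17.5 against 28: 1.96 × √(0.21/17.5 + 0.25/28) = 0.284
- 17.5 against 17.5: 1.96 × √(0.21/17.5 + 0.25/17.5) = 0.318

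**What restriction does not cure.** With true CBR 30%, the same recursion gives a mean observed CBR for the arm of 0.224 when it stops early and 0.263 overall. An arm closed for poor results looks worse than it is, whichever comparator subjects are used.

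**The case against.** The strongest reply is that the contrast carries no decision. Section 9.1.2 disclaims any formal between-arm hypothesis, the chi-square test is conditional, and the error rate, power and futility rules all concern each arm against 30%. This stands, and it limits the weight of the point. A reader might infer that the trial's main conclusions are compromised; the documents do not support that.

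A second reply is that the analysis set for a descriptive difference belongs in the Reporting and Analysis Plan, to which 9.4 defers the details. This stands in part. The protocol nowhere says in terms that subjects enrolled after a closure must enter the difference; that follows from the all-treated population and the absence of a restriction. But the protocol has itself fixed the comparison and its population, so the limit is best stated in the same place.

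Third, the protocol does not present the contrast as purely randomised, because it openly allows pooling of Part 1 subjects. That is correct, and it is a further reason to define the comparison set.

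Fourth, the figures treat Table 5 as binding, although 9.1.2 calls it a guideline. They also assume immediate response, although assessments come every four weeks, and they ignore same-dose Part 1 subjects, who count at the interim looks (9.3.2.1). These points change when an arm closes, not what happens afterwards.

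Two stronger readings should be resisted. One is that a bias of about 5 or 6 points has been shown; any such figure is an assumed drift multiplied by 0.375. The other is that subjects or sites would wait for Arm A to close so as to get the combination. With the median survival of 5.6 or 4.3 months after failure of azacitidine or decitabine cited in 2.1.2, and crossover to the combination at progression (4.6), that is speculation.

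**Conclusion.** The point holds as an inexpensive improvement to a secondary, descriptive comparison. Followed as written, 9.4.1 would mix randomised subjects with later non-randomised ones, and possibly with Part 1 subjects. This is the likely course when one arm is at the null rate and the other at the target: probability 0.71, with about 10.5 of 28 subjects in the open arm non-concurrent on average. It is less frequent when the arms are alike: 0.33 if both are at 30%, 0.19 if both are at 50%.

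These figures rest on binding Table 5 bounds, equal accrual, immediate response, independent arms and Part 2 subjects only. The direction and size of any bias cannot be derived from the documents. A reader might also infer that restricting the comparison makes it unbiased. It does not, because the low estimate in an arm that stopped early remains.

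**What to change.** In 9.4.1, base the Arm A minus Arm B difference in CBR and ORR, its 95% CI and any chi-square test on Part 2 subjects randomised while both arms were open, identified by randomisation date and excluding Part 1. Label the comparison descriptive. Use Part 1 subjects and those enrolled after the other arm closed only in the single-arm results. A difference on all subjects may be shown as supportive if it is labelled non-randomised. Beside the result, note that the estimate for an arm stopped early is biased downwards.

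The cost is a few sentences, a way to identify these subjects in the data, and a wider interval. With about 17 to 18 subjects per arm when A stops early, the approximate half-width rises from 28 to 32 points in the 30%/50% case. The per-arm tests, their error rate and their power do not change. How the randomisation list is handled after a closure is an operational matter and need not be settled in the analysis section.
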